#### **4.2.3 Supportive and sensitivity analyses**

Not applicable.

### **4.3 Secondary endpoint analyses**

All safety analyses will be performed using the SS unless otherwise specified.

#### **4.3.1 Secondary endpoints**

##### **4.3.1.1 Definition of endpoint(s)**

The secondary endpoints are defined as follows:

- Incidence of TEAE
- Incidence of treatment-emergent SAEs
- Incidence of TEAEs leading to discontinuation

Adverse events with a start date prior to the first dose of IMP will be defined as pretreatment AEs. A TEAE is defined as any AE with a start date/time on or after the first dose of IMP or any

unresolved event already present before administration of IMP that worsens in intensity following exposure to IMP.

Missing or partially missing date and/or times will be imputed to determine if an AE is regarded as TEAE using the imputation rule described in [Section 4.5.2](#).

#### **4.3.1.2 Main analytical approach**

An overview of the occurrence and incidence of TEAEs will be provided by BRV formulation (tablet or dry syrup), and overall. The overview will present individual occurrences as well as number and percentage of (unique) participants experiencing each of the following:

- TEAEs
- Treatment-emergent SAEs
- TEAEs leading to discontinuation

[All]

Summaries of the occurrence and incidence of TEAEs, treatment-emergent SAEs and TEAEs leading to discontinuation will be provided by BRV formulation (tablet or dry syrup) and overall. The summary will present individual occurrences as well as number and percentage of (unique) participants, by System Organ Class (SOC) and Preferred Term (PT). These summaries will be provided for the following:

- Incidence of TEAEs
- Incidence of treatment-emergent SAEs
- Incidence of TEAEs leading to discontinuation

[All]

Adverse event summaries will be ordered by alphabetical SOC and decreasing frequency of PT within SOC in the overall column for tables including event counts. For tables including only number and percentage of participants, summaries will be ordered by alphabetical SOC and decreasing incidence of PT within SOC in the overall column.

### **4.4 Exploratory endpoint analysis**

Not applicable.

### **4.5 Other Safety analyses**

All safety analyses will be performed using the SS unless otherwise specified.

#### 4.5.1 Extent of exposure

Exposure will be summarized by Dosing Period, BRV formulation (tablet or dry syrup), and overall. [All]

Administration of IMP will be listed by treatment sequence, and Dosing Period for all participants in the SS and will include the following information: IMP formulation, date/ time of IMP administration and dose. [All]

#### 4.5.2 Adverse events

An overview of the occurrence and incidence of TEAEs will be provided by BRV formulation (tablet or dry syrup), and overall. The overview will present individual occurrences as well as number and percentage of (unique) participants experiencing each of the following:

- Drug-related TEAEs
- Severe TEAEs
- All deaths (AEs leading to death)
- TEAEs leading to death
- TEAEs of special interest

[All]

Summaries of the occurrence and incidence of TEAEs will be provided by BRV formulation (tablet or dry syrup) and overall. The summary will present individual occurrences as well as number and percentage of (unique) participants, by primary SOC and PT. These summaries will be provided for the following:

- Incidence of Drug-related TEAEs
- Incidence of TEAEs leading to death
- Incidence of TEAEs by maximum intensity
- Incidence of TEAEs of special interest
- Incidence of non-serious TEAEs above threshold of 5% of participants

[All]

Summaries by maximum intensity will count each subject at most once within each MedDRA level based on the maximum intensity within that MedDRA level.

Adverse events with missing intensity will be considered as 'Severe' events for summary purposes but recorded as missing in the listings. Adverse events with missing causal relationship to IMP will be considered as 'Related' for the tabulations but presented as missing in the listings. For the summary of non-serious TEAEs above threshold of 5% of participants, only TEAEs which are reported in above 5% of participants within a BRV formulation (tablet or dry syrup) will be included.

Adverse event summaries will be ordered by alphabetical SOC and decreasing frequency of PT within SOC in the overall column for tables including event counts. For tables including only number and percentage of participants, summaries will be ordered by alphabetical SOC and decreasing incidence of PT within SOC in the overall column.

A listing will be presented by treatment sequence, dosing period at onset, BRV formulation (tablet or dry syrup) and participant for all AEs for the ES. This will include reported term, SOC, PT, the onset date/time and outcome date/time of the event (including relative days or

ongoing if applicable), the AE duration, pattern of event, intensity, relationship, action taken and outcome. In addition, the listing will flag TAEs, SAEs, AEs leading to discontinuation and AEs of special interest. [All]

A glossary of AE terms including reported term, SOC and PT will also be presented. [All]

Imputed dates will not be shown in the listings; all dates will be displayed as reported in the database.

The following rules will be applied for partial start dates and time:

- If only the month and year are specified and the month and year of the first dose of IMP is not the same as the month and year of the start date, then use the 1st of the month, or the date of Screening if this is later (if the latter imputation results in an end date that is earlier than the start date, then use the 1st of the month). If time is missing this will be imputed as 00:00 h
- If only the month and year are specified and the month and year of the first dose of IMP is the same as the month and year of the start date, then use the date of the first dose of IMP. If this results in an imputed start date that is after the specified end date, then use the 1st of the month, or the date of Screening if this is later (if the latter imputation results in an end date that is earlier than the start date, then use the 1st of the month). If the imputed date is the date of dosing then time will be imputed as the start time of the dosing (i.e., event will be regarded as treatment-emergent)
- If only the year is specified, and the year of the first dose of IMP is not the same as the year of the start date then January 01 will be used. If time is missing this will be imputed as 00:00 h
- If only the year is specified, and the year of the first dose of IMP is the same as the year of the start date, then the date of the first dose of IMP will be used. If this results in an imputed start date that is after the specified end date, then January 01, or the date of Screening if this is later will be used (if the latter imputation results in an end date that is earlier than the start date, then January 01 will be used). If the imputed date is the date of first dose of IMP then time will be imputed as the start time of the study medication intake (i.e., event will be regarded as treatment-emergent)
- If the start date is completely unknown, then use the date of dosing. If this results in an imputed start date that is after the specified end date, then use January 01 of the year of the end date, or the date of Screening if this is later.

The following rules will be applied for partial end/stop dates:

- If only the month and year are specified, then use the last day of the month
- If only the year is specified, then use December 31 of the known year
- If the stop date is completely unknown, do not impute the stop date

Missing or partially missing date and/or times will be imputed as described in [Table 4-3](#) for the calculation of duration of each AE. AE duration is computed and reported in day and time format.

**Table 4-3: Calculation Rules for Duration of AEs**

Data Availability	Onset Date/Time	Outcome Date/Time	Calculation Rules
Complete data	D1/T1	D2/T2	Duration = (D2-D1)*24+(T2-T1)
End time missing	D1/T1	D2/--	End time is substituted by time 23:59h (=23.98 in decimal format). Duration=<(D2-D1)*24+(23.98-T1)
Start time missing	D1/--	D2/T2	Onset time is substituted by 00:00h. Duration=<(D2-D1)*24+T2
Start and end time missing	D1/--	D2/--	Duration=<[(D2-D1)+1]*24
Start day and time missing	--/--	D2/T2	Duration=<(D2-D0)*24+(T2-T0) For a participant in the SS, D0 and T0 are the date and time of the first administration of study medication and for screen failures, D0 is the date of the Screening Visit date and T0=00:00h.
End day and time missing	D1/T1	--/--	If the stop date is missing, duration will not be calculated.
Start and end date missing	--/--	--/--	If the stop date is missing, duration will not be calculated.

The duration of each AE will be calculated as follows and will be presented in dd:hh:mm format where dd represent days, hh: hours, and mm: minutes:

$$\text{Duration of AE} = \text{End date/time of AE} - \text{Start date/time of AE}$$

Adverse events will be assigned to Dosing Periods, based on the onset date/ time of the AE. Assignment to Dosing Periods will be done after missing dates have been imputed as described above. AE will be assigned to a treatment based on the treatment received in the Dosing Periods as follows:

- Dosing Period 1: the start date/time is on or after IMP administration in Dosing Period 1 and prior to IMP administration in Dosing Period 2.
- Dosing Period 2: the start date/time is on or after IMP administration in Dosing Period 2.

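### SAP 4.5.2 has no classification rule for an adverse event with a known onset date but no time, and its partial-date rule sends same-month Period 2 events to the Period 1 formulation

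*SAP*

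**What the plan says.** SAP 4.3.1.1 defines a TEAE by start date and time relative to the first dose, and a pretreatment AE by start date only. For incomplete onsets it points to Section 4.5.2: missing parts "will be imputed to determine if an AE is regarded as TEAE using the imputation rule described in" that section. It does not say which of the rules in 4.5.2 it means.

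Section 4.5.2 holds two sets of rules.

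- **Partial start dates.** The list covers onsets known only by month, only by year, or not at all. For a month-only onset in the month of the first dose the instruction is "then use the date of the first dose of IMP". If the imputed date is the dosing date, "then time will be imputed as the start time of the dosing (i.e., event will be regarded as treatment-emergent". A month-only onset in any other month takes the 1st of that month (or the Screening date if later), at 00:00.
- **Table 4-3.** The lead-in is "Missing or partially missing date and/or times will be imputed as described in" this table, for the calculation of each event's duration. The table's title is "Table 4-3: Calculation Rules for Duration of AEs". Its row for a missing start time reads "Onset time is substituted by 00:00h".

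Events are then placed in a Dosing Period by comparing onset date and time with dosing in each period. On the order of steps the SAP says "Assignment to Dosing Periods will be done after missing dates have been imputed as described above". That sentence mentions dates but not times.

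**The concern.** A complete date with no time is the simplest kind of incomplete record, and the classification list omits it. A programmer told to impute missing times under 4.5.2 finds one rule that fits, 00:00, and on a dosing day 00:00 is before the morning dose. An event known to have occurred on Day 1 could then be treated less cautiously than one known only by month, which is set to the dose time and counted. That runs against the SAP's general approach: 4.5.2 also counts missing intensity as severe and missing causality as related.

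The partial-date rule is a separate matter. It anchors on the first dose of the study, which suits a parallel-group trial. In this crossover both periods can fall in one calendar month, and the period determines the formulation. The rule uses the stop date only to reject an impossible start, never to ask whether Period 2 is possible.

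At stake is the incidence of TEAEs by formulation, the secondary endpoint.

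**Working it through.** The plan gives no figure for this point, so the check is a trace of the rules.

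**1. Untimed onset on a complete date, if 00:00 is used for classification.** The dose time is not in the documents; I assumed 08:00 or 09:00, and both give the same result. Period 2 starts 2 days (Day 1 to Day 3) plus 6 to 10 days of wash-out after the first dose, so 8 to 12 days later. Take a first dose on 4 March and the shortest gap, so that Period 2 starts on 12 March.

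| Untimed onset | Placed at | Result |
|---|---|---|
| 4 March (Period 1, Day 1) | before first dose | not a TEAE by date/time |
| 12 March (Period 2, Day 1) | before Period 2 dose | Period 1 formulation |
| 13 March (Period 2, Day 2) | after Period 2 dose | Period 2, correct |

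The first event is not pretreatment under the date-only definition either, so it fits neither class. Only the first dosing day of each period is affected.

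**2. Month-only onset.** I traced 366 daily first-dose dates (one leap year), wash-outs of 6, 8 and 10 days, and one onset on each of 11 days from the first Period 2 dose into follow-up. Even spread of onsets is an assumption. This gives 366 × 11 = 4,026 Period 2 onsets per wash-out.

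An onset reaches Period 2 correctly only if the 1st of its month falls after the Period 2 first-dose date. For each month start, with Period 2 beginning d = 1 to 10 days earlier, there are 11 − d such onsets. They sum to 55, and 12 month starts × 55 = 660. So 4,026 − 660 = 3,366 go to Period 1, and 3,366 / 4,026 = 83.6%.

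| Wash-out | Same month as first dose: sent to Period 1 | Later month: onsets | Later month: correct | Later month: sent to Period 1 |
|---|---|---|---|---|
| 6 days | 100% of 2,310 | 1,716 | 660 (38.5%) | 61.5% |
| 8 days | 100% of 2,046 | 1,980 | 660 (33.3%) | 66.7% |
| 10 days | 100% of 1,782 | 2,244 | 660 (29.4%) | 70.6% |

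No true Period 1 onset was misplaced. The stop-date fallback, which can make an event pretreatment, was not modelled. By the same logic, a year-only onset in the year of the first dose takes the first-dose date and so goes to Period 1. For a wholly unknown start the SAP says to use the date of dosing without saying which period.

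**3. Size per participant.** One participant is 1/60 = 1.7 percentage points with 60 per formulation, 1/64 = 1.6 with the 64 planned for Cohort 1, and 1/96 = 1.0 with the full 96.

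**The case against.** The strongest objection is that Table 4-3 is a duration table by its lead-in and its title, so the SAP never orders 00:00 for TEAE status or period. This stands. A reader might infer that the SAP sets untimed Day 1 onsets to midnight and so removes them from the TEAEs; the text does not support that as a stated rule. The dosing-time provision for partial dates also points to the opposite intent. What remains is that 4.3.1.1 promises a rule for missing times and 4.5.2 supplies none for classification. The result is either the 00:00 reading or unguided discretion in an open-label study.

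A reader might also infer that every month-only date goes to Period 1. That is wrong: onsets in a later month take the 1st and can land correctly in Period 2 (about 29% to 38% in the trace). A Period 2 first dose on the 1st itself does not help, because 00:00 precedes the morning dose.

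Other points stand in part:

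- An untimed Day 1 event that truly began before dosing is placed correctly by 00:00.
- Participants are confined from Day -1 to Day 4, so missing Day 1 times should be rare.
- The Data Evaluation Meeting (protocol 9.5) can handle missing values case by case, and AE listings show dates as reported, so no event vanishes from the record.
- In Pool Phase 1, 80.4% of BRV participants had a TEAE. Many reclassified events would therefore not change the overall incidence row.
- Assigning the latest possible period would misplace some long Period 1 events. That is a real cost of the remedy, and the fix below allows for it.

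**Conclusion.** Two separate defects hold, both minor. First, there is no classification rule for a complete onset date with no time. If the duration rule fills the gap, first-dosing-day events can leave the TEAEs (Period 1) or move to the other formulation (Period 2). This is a plausible reading, not an express instruction. Second, the stated partial-date rule sends every month-only Period 2 onset in the month of the first dose to the Period 1 formulation, even when the stop date leaves Period 2 open. Later-month onsets may fall in either period.

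The size is at most about 1.0 to 1.7 percentage points per affected participant, and only where that participant has no other event in the same row. Misplacement between periods runs one way, from Period 2 to Period 1. Because sequence is randomised, it blurs the formulation comparison and does not favour either formulation in expectation. The documents give no count of incomplete records; with in-clinic dosing it is probably near zero. The tables are descriptive and do not enter the bioequivalence decision.

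**What to change.** Amend SAP 4.5.2 as follows.

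1. State that the 00:00 row of Table 4-3 applies to duration only.
2. If the onset date is the first dosing day of either Dosing Period and the time is missing, set onset to that period's first dose time, unless the stop date/time or other recorded data show an earlier onset.
3. If a partial onset date is compatible with both periods, do not default to the first dose of the study. Use the stop date to assign the latest compatible period. Flag these records or show the alternative assignment, because a long Period 1 event could otherwise be placed in Period 2 unseen.

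The cost is a few sentences, one change to the AE derivation and a flag in the listing. No new data are needed, and the primary analysis does not change.

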#### 4.5.3 Additional safety assessments

##### 4.5.3.1 Clinical laboratory evaluations

Laboratory parameters will be grouped according to Appendix 2 of the protocol. All clinical laboratory parameters will be listed by treatment sequence, participant, variable and period/visit, changes from Baseline (as defined in [Section 4.1.2](#)) for continuous values, flags for

measurements outside the reference ranges, and relative day (calculated as described in [Section 4.1.1.1](#)) for the RS. The listing will include the BRV formulation (tablet or dry syrup) received at the time of measurement if applicable (the treatment received in the corresponding Dosing Period will be assigned).

For the flags for results that are out of reference range, values that are below the lower limit of the reference range will be flagged as 'L' (low) and values that are above the upper limit of the reference range will be flagged as 'H' (high).

Any laboratory variable that are given as '<xx' or '>xx' in the database will be imputed with the absolute value of the number without the sign (e.g., <2.2 will be imputed as 2.2) for the calculation of descriptive statistics and changes from Baseline.

[All]

Additional laboratory tests including serology, alcohol detect test, and urine drug screen will be listed for the ES. [All]

#### **4.5.3.1.1     Laboratory values over time**

For clinical laboratory parameters (hematology and clinical chemistry), observed results and changes from Baseline will be summarized using descriptive statistics by BRV formulation (tablet or dry syrup) at scheduled time point, as applicable. [All]

#### **4.5.3.1.2     Individual participant changes of laboratory values**

Shift tables from Baseline to post-Baseline scheduled time point will be presented by BRV formulation (tablet or dry syrup). These summaries will present a cross-tabulation of Baseline values against post-Baseline values categorized as below reference range, within reference range and above reference range. Each cell will include the corresponding number and percentage of participants. [All]

#### **4.5.3.1.3     Potential drug-induced liver injury**

A separate listing will present all visits including unscheduled visits for participants who has any incident of ALT and/or AST $\geq$ 3x Upper limit of normal (ULN), Total bilirubin  $\geq$ 1.5x ULN or ALP  $>$  1.5 x ULN.

The listing will display visits for which at least one of the above criteria was fulfilled for a given participant and will display all of the following results obtained at that visit for the specified parameters for the SS.

- Potential hepatotoxicity with hepatitis
- Potential hepatotoxicity with hypersensitivity
- ALT and/ or AST  $\geq$ 3x ULN and Total bilirubin  $\geq$ 1.5x ULN at any same visit
- ALT and/ or AST  $\geq$ 3x ULN and Total bilirubin  $\geq$ 2x ULN at any same visit
- ALT and/ or AST  $\geq$ 3x ULN, Total bilirubin  $\geq$ 2x ULN and ALP  $<$ 2x ULN at any same visit

[All]

A summary of participants who met the following criteria will be presented by BRV formulation (tablet or dry syrup) and in total. [All]

- Potential hepatotoxicity with symptoms potentially associated with hepatitis or hypersensitivity
- Potential hepatotoxicity without symptoms potentially associated with hepatitis or hypersensitivity
- ALT and/ or AST  $\geq 3$  x ULN and Total bilirubin  $\geq 1.5$  x ULN at any same visit
- ALT and/ or AST  $\geq 3$  x ULN and Total bilirubin  $\geq 2$  x ULN at any same visit
- ALT and/ or AST  $\geq 3$  x ULN, Total bilirubin  $\geq 2$  x ULN and ALP  $< 2$  x ULN at any same visit

A summary of participants who met the following criteria at any visit will be presented by BRV formulation (tablet or dry syrup) and in total. In addition, individual occurrences will be shown. [All]

- AST  $\geq 3$  x ULN
- AST  $\geq 5$  x ULN
- AST  $\geq 8$  x ULN
- AST  $\geq 10$  x ULN
- AST  $\geq 20$  x ULN
- ALT  $\geq 3$  x ULN
- ALT  $\geq 5$  x ULN
- ALT  $\geq 8$  x ULN
- ALT  $\geq 10$  x ULN
- ALT  $\geq 20$  x ULN
- AST or ALT  $\geq 3$  x ULN
- AST or ALT  $\geq 5$  x ULN
- AST or ALT  $\geq 8$  x ULN
- AST or ALT  $\geq 10$  x ULN
- AST or ALT  $\geq 20$  x ULN
- Total bilirubin  $\geq 1.5$  x ULN
- Total bilirubin  $\geq 2$  x ULN
- ALP  $\geq 1.5$  x ULN
- New ratio value (ALT or AST, whichever produced the highest x ULN/ ALP x ULN value) of 5 or greater

By-participant listings of suspected hepatic events will be presented for the SS. [All]

By-participant listings of family DILI-relevant medical history for PDILI will be presented for the RS. [All]

By-participant listings of information related to potential hepatic event will be presented by treatment sequence, and time point and BRV formulation (tablet or dry syrup) for the SS. [All]

Time course for liver function tests (AST, ALT, ALP and Total bilirubin) will be displayed superimposed in a single plot by participant for participants meeting a criterion, ALT and/ or AST  $\geq 3$  x ULN, Total bilirubin  $\geq 2$  x ULN and ALP  $< 2$  x ULN at any same visit from the SS. [All]

#### **4.5.3.2 Vital signs**

The following vital signs measurements will be obtained: Systolic Blood Pressure (SBP), Diastolic Blood Pressure (DBP), pulse rate, respiratory rate and body temperature.

##### **4.5.3.2.1 Vital sign values over time**

Vital signs variables and changes from Baseline will be summarized using descriptive statistics by BRV formulation (tablet or dry syrup) at each scheduled time point. [All]

##### **4.5.3.2.2 Individual participant changes of vital sign values**

By-participant listings of all vital sign variables and change from Baseline will be presented by treatment sequence, period, visit, BRV formulation (tablet or dry syrup) and time point for the RS. [All]

#### **4.5.3.3 Electrocardiograms**

The following twelve-lead ECG variables will be obtained: heart rate, PR, QRS, QT intervals, and QTcF.

